Participants who complete Cycle 24 of the Treatment Phase and did not meet withdrawal criteria (Section 7) are eligible to participate in the LTFU Phase. Eligible participants will continue taking the last dose assigned in the Treatment Phase (approximately 2 mg/m² BID [maximum dose of 4mg BID]) of PD-0325901 (mirdametinib; open-label study treatment), on an intermittent (3 weeks on/1 week off) dosing schedule in 28-day cycles. Participants will remain in the LTFU Phase until a withdrawal criterion is met as described in Section 7 or mirdametinib is commercially available. Refer to the schedule of activities ([SoA] Section 1.4) for the required assessments for the LTFU Phase.

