2.1 Study Objectives

Table 1: Study Objectives and Endpoints

Objectives	Endpoints
Primary	
To evaluate the confirmed complete and partial response (CR + PR) rate of mirdametinib using volumetric magnetic resonance imaging (MRI) analysis, as assessed by a blinded independent central review (BICR), in participants with an inoperable NF1 associated PN that is causing significant morbidity.	Objective response rate at the end of the Treatment Phase (defined as PN decrease ≥ 20% compared to baseline in consecutive scans 2-6 months apart) using centrally read MRI volumetric analysis.

Document: S:\Q_146\Q_03974\MEK-NF-201\Prog_Stat\Documentation\SAP\MEK-NF-201 SAP v1.0.0.docx

Secondary	
-	Cofety and points will include incidence of
To evaluate the safety and tolerability of mirdametinib in participants with NF1 and symptomatic inoperable PN as measured by the incidence of adverse events (AEs)	Safety endpoints will include incidence of treatment-emergent adverse events, changes in laboratory parameters, vital signs, physical examination findings, and electrocardiograms (ECGs); Incidence of treatment-emergent adverse events will also be assessed by dose formulation.
	Tolerability will be assessed according to toxicities graded by National Cancer Institute (NCI) Common Terminology Criteria for Adverse Events (CTCAE) Version (v) 5.0;
To determine the duration of response (DoR)	Duration of response for participants whose best overall confirmed response is complete response (CR) or partial response (PR) using centrally read MRI volumetric analysis
To evaluate the effect of mirdametinib on quality of life as measured by patient-reported outcomes (PROs)	Change from baseline in quality of life (QoL) assessed by the age-specific Pediatric Quality of Life Inventory
	The number of participants with a meaningful score change as derived from the anchor analysis.
To evaluate the effect of mirdametinib on pain as measured by PROs	Change from baseline in pain assessed using the Numeric Rating Scale-11 and Pain Interference Index (PII)
	The number of participants with a meaningful score change as derived from the anchor analysis.
Exploratory	
To evaluate the effect of mirdametinib on physical functioning as measured by PROs	Change from baseline in physical function status (Patient-Reported Outcomes Measurement Information System [PROMIS] - Physical Function/Mobility/Upper Extremity Scale) in the Treatment Phase

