2.2 Study Design

MEK-NF-201 is a multi-center, open-label, single-arm, longitudinal, uncontrolled, Phase 2b study to evaluate the efficacy, safety, and tolerability of mirdametinib in participants ≥ 2 years of age with an inoperable NF1-associated PN that is causing significant morbidity.

This study will consist of two phases: the Treatment Phase and the optional Long-Term Follow-Up (LTFU) Phase. Approximately 100 participants will be enrolled and stratified by age (approximately 50 participants 2 to 17 years of age and 50 participants ≥ 18 years of age). The first five participants enrolled in the pediatric cohort must be 9 to 17 years of age at the time of signing informed consent/assent. After the first 5 participants have enrolled in the pediatric cohort, enrollment into this cohort will be paused, and only after Data Monitoring Committee (DMC) evaluation of at least 2 cycles of cumulative safety data for these 5 participants will the pediatric cohort be re-opened and potentially expanded down to 2 years of age. Note the adult cohort will not be affected by this special procedure; participants ≥ 18 years of age will be enrolled continuously from the outset.

Document: S:\Q_146\Q_03974\MEK-NF-201\Prog_Stat\Documentation\SAP\MEK-NF-201 SAP v1.0.0.docx

Participants will be screened for up to 45 days prior to the first dose of study treatment (mirdametinib) and eligibility will be based on the inclusion and exclusion criteria listed in Sections 5.1 and 5.2 of the protocol, respectively. Study treatment will then be administered orally at a dose of 2 mg/m² BID with a maximum dose of 4 mg BID. Dosing in the Treatment Phase will be on a 28-day cycle with a 3 week on/1 week off schedule for up to 24 Cycles. Eligible participants will take their first dose of study treatment following all pre-dose assessments on Cycle 1 Day 1. All participants will remain in the Treatment Phase of the study until radiographic disease progression (confirmed by central review), they discontinue study treatment for any other reason, the study is stopped by the sponsor for any reason, or the participant has completed the study through Cycle 24.

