4.2.1.1 Adverse Event Definitions

Certain AEs are specified as adverse events of special interest (AESI). AESIs for this study were marked by the investigators and will be reported as such. AESIs include but are not limited to the following cases in Table 8.

Table 8: Adverse Events of Special Interest

Gastrointestinal (reported as AESI if Grade ≥3)		
Diarrhea	Nausea	Vomiting
Eye Disorders (reported as A		
Retinal Vein Occlusion (RVO)		Optic neuropathy
Retinopathy	Retinal detachment	
Cardiac Disorders (reported as AESI if Grade ≥2)		
Ejection fraction decreased		Left ventricular dysfunction
Neurological Disorders (reported as AESI if Grade ≥2)		
Confusion	Hallucinations	Delirium
Infections and Infestations (r	eported as AESI if Grade ≥3)	
Viral Rash		
Skin Disorders (reported as AESI if Grade ≥3)		
Rash*	Acneiform Rash*	

^{*}Rash and Acneiform Rash were considered an AESI for Grade ≥2 in earlier versions of the protocol. Due to this, there may be some Grade 2 rashes marked as AESIs by the investigators, which will be reported as such.

The AESI of "Rash" is a composite term, all PTs which will be considered as a "Rash" AESI are listed in Appendix 2.

AEs will be summarized combined across the Treatment and LTFU phases. A TEAE is defined as an AE that starts or worsens on or after the first dose of study treatment is taken, including those occurring or increasing in severity up to 30 days after the last dose of study treatment.

A treatment-emergent serious adverse event (SAE) is defined as a TEAE that, at any dose; results in death; is life-threatening; requires inpatient hospitalization or prolongation of existing hospitalization; results in persistent disability/incapacity; is a congenital anomaly/birth defect; or is assessed by the investigator as an otherwise important serious medical event.

Document: S:\Q_146\Q_03974\MEK-NF-201\Prog_Stat\Documentation\SAP\MEK-NF-201	SAP
v1.0.0.docx	
Author	

An AE will be classified as a study treatment-related AE if it has an investigator determination of related to study treatment. Investigators will provide their assessment as related to study treatment, not related to study treatment, or not applicable. AEs that are missing a treatment related/unrelated classification will not be imputed and "missing" will be presented as a category in summary tables.

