4.3.7 Exposure to Study Treatment

There is only a single dose level on this study. All participants receive mirdametinib at a dosage level of approximately 2 mg/m² BID (up to a maximum of 4 mg BID). All participants follow an intermittent dosing schedule of 3 weeks on/1 week off, which creates 28-day cycles. The Treatment Phase comprises 24 cycles.

Participants enrolled in the LTFU Phase of the study continue taking the last dose assigned in the Treatment Phase (approximately 2 mg/m² BID [maximum dose of 4 mg BID]) of mirdametinib, unless a dose modification is required (e.g., body surface area [BSA] change), on an intermittent (3 weeks on/1 week off) dosing schedule in 28-day cycles. This phase is of indefinite length.

At any point in the study, if a participant exhibits sufficiently worrisome AEs of significant toxicity, dosing can be interrupted and/or reduced. If dose is reduced, then it may only be increased in the Treatment Phase following a BSA change and with approval from the medical monitor and sponsor. The criteria for dose reduction, and the reduced dose plan are in Section 6.6 of the protocol.

The following exposure-related measures will be summarized:

Document: S:\Q_146\Q_03974\MEK-NF-201\Prog_Stat\Documentation\SAP\MEK-NF-201 SAP v1.0.0.docx Author:

SpringWorks Therapeutics Protocol Number: MEK-NF-201

- Duration of exposure (months)
- Total duration of exposure (participant years)
- Time to first dose reduction (months)
- Participants with dose modification along with reasons for dose modification
- Participants with dose reduction along with reasons for dose reduction
- Participants with dose interruption along with reasons for dose interruption
- · Actual dose intensity
- Relative dose intensity

Duration of exposure in months is calculated as (Date of last dose - Date of first dose +1)/30.4375.

Total duration of exposure in participant years is calculated as (total sum of all participants duration of exposure in months)/12

Time to first dose reduction in months is calculated as (Date of first dose reduction - Date of first dose + 1)/30.4375

Actual and relative dose intensity will be calculated as follows:

- Actual dose intensity cumulative dose received/number of prescribed dosing days.
- Relative dose intensity 100*(cumulative dose received/planned dose).

Cumulative dose received will be calculated using dispensed and returned pill counts. Actual dose intensity will also be derived accounting for BSA.

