6.12.1.7 Evaluate Key Safety by Formulation

AEs by SOC and PT, and PT only will be assessed split by formulation. The following groupings will be used:

- Pediatrics receiving tablets
- Pediatrics receiving capsules
- Combined pediatrics and adults receiving capsules
- All participants

The summaries provided will mirror the summary of all TEAEs presented by SOC and PT, and PT only as described in Section 6.12.1.1.

Document: S:\Q_146\Q_03974\MEK-NF-201\Prog_Stat\Documentation\SAP\MEK-NF-201 SAP v1.0.0.docx

Author:

Changes to the Planned Analyses

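### TEAE percentages pool the 24-cycle Treatment Phase with an open-ended LTFU Phase; a Treatment-Phase-only version and a rule for assigning events to a formulation should be added

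*SAP*

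**What the plan says.** SAP 4.2.1.1 sets one reporting period for adverse events: "AEs will be summarized combined across the Treatment and LTFU phases". The two phases differ in kind. SAP 4.3.7 says of the first, "The Treatment Phase comprises 24 cycles", and of the second, "This phase is of indefinite length". Protocol 4.1 makes LTFU optional and gives its end only as an event: "Participants will remain in the LTFU Phase until a withdrawal criterion is met as described in Section 7 or mirdametinib is commercially available".

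The percentages are head counts. SAP 6.12.1.1 bases them on participants at risk. SAP 5.1.2 defines at risk as being in the analysis set and having entered the period. SAP 4.2.1.2 counts a preferred term once per participant, whenever it occurs. Event counts are also shown, without a time denominator.

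The SAP lists a formulation split under its secondary safety endpoint (Table 1): "Incidence of treatment-emergent adverse events will also be assessed by dose formulation". SAP 6.12.1.7 names four groups: children on tablets, children on capsules, children and adults on capsules combined, and everyone. On content it says "The summaries provided will mirror the summary of all TEAEs presented by SOC and PT, and PT only". It does not say where a child who received both formulations belongs, or which formulation an event is charged to.

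Two planned outputs do bring in time. SAP 6.12.1.1 summarizes TEAEs by cycle of first onset (single cycles to 6, then 7 to 12, then 13 and later). SAP 4.3.7 and 6.9 summarize duration of exposure and participant-years.

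**The concern.** A crude percentage counted over a window without an end grows with follow-up. Two columns can be compared at face value only if their follow-up is similar, and pooling LTFU removes the natural 24-cycle cap that would have kept it so. The percentages also depend on the cutoff: the same participants, summarized later, show higher figures.

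There are grounds to expect unequal LTFU time. SAP 2.2 pauses the pediatric cohort after its first 5 participants, pending DMC review, and states that "participants ≥ 18 years of age will be enrolled continuously from the outset". Ages 2 to 8 open only after that review (Protocol 1.3, footnote 1).

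The formulation table has a second gap. Protocol 6.1.1 makes the capsule the default and the tablet available on request, and neither describes nor forbids a change. A child who had both would fit both pediatric labels in SAP 6.12.1.7, and events on one formulation could appear under the other.

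At stake is how a reader interprets the age-cohort and formulation columns. No test or efficacy conclusion depends on them.

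**Working it through.** **The plan's own safety figure.** Protocol 9.2 and SAP 2.3 give a 95% chance of seeing at least one event with a 3.0% rate in 100 participants. Check: 1 − 0.97^100 = 0.952, so it is reproduced. The 3.0% carries no time window, so this figure does not bear on pooling.

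**Inputs from the documents.** Treatment Phase: 24 × 28 = 672 days; 672 / 365.25 × 12 = 22.1 months. LTFU: no fixed length. The documents give no event rate, cutoff date, LTFU uptake, exposure by column or number of participants who changed formulation. Everything below is therefore an illustration under stated assumptions.

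**Constant hazard, equal in both columns (assumed).** Crude incidence = 1 − exp(−h × t), with 22 versus 34 months (12 months' difference in LTFU, assumed):

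| Monthly hazard | 22 months | 34 months |
|---|---|---|
| 1% | 1 − exp(−0.22) = 20% | 1 − exp(−0.34) = 29% |
| 2% | 1 − exp(−0.44) = 36% | 1 − exp(−0.68) = 49% |
| 5% | 1 − exp(−1.10) = 67% | 1 − exp(−1.70) = 82% |

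Anchored instead on an event with 20.0% incidence over the 24 cycles, the pooled figure is 24.7%, 29.1% and 37.2% with 6, 12 and 24 extra months. With 12 extra months, events of 5%, 10% and 40% become 7.6%, 15.0% and 54.5%. Restricted to the 24-cycle window, every column returns its starting value.

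**Front-loaded events, equal risk (assumed).** Take 5% per month for 6 months, then 0.5% per month.
- 22 months: cumulative hazard 0.30 + 16 × 0.005 = 0.38; incidence 1 − exp(−0.38) = 31.6%.
- 34 months: 0.30 + 28 × 0.005 = 0.44; incidence 1 − exp(−0.44) = 35.6%.

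The gap is 4 points.

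**Would a participant-year rate be enough?** In the front-loaded example, expected time at risk per person is [1 − exp(−0.30)] / 0.05 = 5.18 months for the first six months. The later part adds exp(−0.30) × [1 − exp(−0.08)] / 0.005 = 11.39 months at 22 months, or exp(−0.30) × [1 − exp(−0.14)] / 0.005 = 19.36 months at 34.
- 22 months: 0.316 / (16.57 / 12) = 22.9 first events per 100 participant-years.
- 34 months: 0.356 / (24.54 / 12) = 17.4.

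Risk is identical, yet the longer-followed group looks about 24% safer (17.4 / 22.9 = 0.76). The rate removes the distortion only when the hazard is constant.

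**Limit of the 24-cycle window.** It caps follow-up but does not equalize early discontinuation. With the 20% event (h = −ln 0.80 / 22.08 = 0.0101 per month), if half a column left at 6 months (assumed), it would show 0.5 × 5.9% + 0.5 × 20.0% = 12.9%. Exposure therefore needs to appear beside each column.

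**Children on both formulations.** With 50 children and an assumed 3, 5 or 10 who took both, the tablet and capsule pediatric denominators would sum to 53, 55 or 60.

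**The case against.** The plan does not disregard time on drug, though a reader of SAP 4.2.1.1 alone might infer that it does. The onset-by-cycle table puts the age cohorts in the same bounded windows through Cycle 12, and the exposure summary would reveal an imbalance between them. This stands. It is only a partial answer, because the last onset band, Cycle 13 and later, runs into LTFU without end, and neither output is planned by formulation.

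A reader might also infer that follow-up is unequal by design. The documents do not support that. Every participant has the same 24-cycle maximum, the pause covers one DMC review of at least 2 cycles in 5 children, and adult accrual could run longer than pediatric accrual. Neither the direction nor the size of any gap is known. That tablet users are mainly the youngest children is likewise an inference.

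Double counting is argued from silence. The P-OMAQ reminder repeated into LTFU fits a late start on tablets, but fits a missed questionnaire equally well.

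Finally, the study is single-arm, no column is tested against another, and the formulation groups overlap by construction. The formulation split is in the SAP's endpoint table but not in the protocol's. All of this stands and limits the point to how descriptive tables are read. Against it, SAP 6.6 and 6.7 already present concomitant medications and procedures by phase, so a phase-specific AE view would follow the plan's own practice.

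**Conclusion.** The point holds as a reporting weakness. Crude TEAE percentages over an open-ended window mix risk with length of follow-up and depend on the cutoff, and the formulation table lacks a rule for participants or events that cross formulations. If LTFU time differed by 12 months between columns, equal risk could appear as a 9- to 15-point gap at constant hazards of 1% to 5% per month, or about 4 points in the front-loaded example. Those follow-up times and hazards are assumptions; the actual gap could be nil.

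It would go too far to conclude that the formulation comparison cannot be informative, or that children will be counted twice. The documents establish neither unequal exposure nor any change of formulation. The primary endpoint is unaffected.

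**What to change.** 1. In SAP 6.12.1.1 and 6.12.1.7, present the TEAE overview and the SOC/PT tables for the Treatment Phase alone, by age cohort and by formulation, beside the pooled version. SAP Table 10 already closes Cycle 24 at study day 672, which gives a ready cut.
2. Show participant-years for each formulation column.
3. In 6.12.1.7, assign each TEAE to the formulation being taken at onset, and show any participant who received both formulations separately. In LTFU, where no dosing diary is kept, dispensing records would determine the formulation.
4. Rates per 100 participant-years may be added as a supplement only, with the constant-hazard limitation stated.

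The cost is programming and additional tables. No new data are needed: Protocol 6.1.1 has the formulation requested through the IRT, and Protocol 6.4 records capsules and tablets dispensed and returned in the eCRF.

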4.2.1.2 Coding of Adverse Event Terms

The AE term (Investigator term) will be assigned to the lowest level term (LLT), and a preferred term (PT) will be classified by a high-level term (HLT), a high-level group term (HLGT), and a system organ class (SOC) according to the Medical Dictionary for Regulatory Activities (MedDRA) thesaurus, Version 24.0 or higher, depending on the latest version available during the study.

Although there can be multiple SOCs for a PT, each PT will be linked with one SOC, namely the primary SOC that is automatically assigned by MedDRA via one HLT, HLGT route.

The following coding data will be presented:

- LLT (Investigator term).
- PT.
- Coding data per primary SOC:
 - · HLT.
 - HLGT.

In the event that no coding information is available for a specific AE, the AE will be presented as an 'Uncodable Event' in all summary tables.

AEs will be reported on a per-participant basis and per-event. On a per-participant basis, this means that even if a participant reported the same event repeatedly (i.e., events mapped to the same PT) during the study period, the event will be counted only once. In the latter case, the event will be assigned the worst severity and the strongest relationship to the study treatment. The earliest date will be regarded as start date of the event and the latest date/time will be regarded as stop date of the event within the assigned study period.

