2.1. Study Rationale

Protocol MEK-NF-201 is an open-label, multi-center, Phase 2b study being conducted to determine the efficacy and safety of mirdametinib (PD-0325901) in participants \geq 2 years old with symptomatic inoperable NF1-associated PNs. A Phase 2 study with PD-0325901 was previously conducted in NF1-associated plexiform neurofibromas (Weiss, 2017). This Phase 2, open-label study evaluated 19 participants (range 16 to 39 years) with symptomatic or progressing plexiform neurofibromas. Quantitative radiographic response in a target PN after administration of PD-0325901 at a dose 2 mg/m² BID (maximum dose of 4 mg BID) on a 3 weeks on/1 week off schedule was assessed. Overall, PD-0325901 was well tolerated; five subjects (26.3%) developed Grade 3 toxicities, with four of those subjects (21%) reporting a Grade 3 toxicity of pain. No subjects developed Grade 4 or higher toxicities and 1 subject experienced a SAE. This study demonstrated activity of PD-0325901 in subjects with a PN with eight participants (42.1%; 95% confidence interval [CI]: 20%, 67%) responding to PD-0325901 as defined by a \geq 20% reduction of the target PN after 1 year of therapy.

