1.1 Rationale

MEK-NF-201 is an open-label, multi-center, Phase 2b study being conducted to determine the efficacy and safety of mirdametinib (PD-0325901) in participants ≥ 2 years old with symptomatic, inoperable, neurofibromatosis type 1 (NF1)-associated plexiform neurofibromas (PNs).

A Phase 2 study with mirdametinib was previously conducted in participants with NF1-associated PNs (Weiss, 2021). This Phase 2, open-label study evaluated 19 participants (range 16 to 39 years) with symptomatic or progressing PNs. Quantitative radiographic response in a target PN after administration of mirdametinib at a dose 2 mg/m² twice daily (BID) (maximum dose of 4 mg BID on an intermittent (3 weeks on/1 week off) dosing schedule in 28-day cycles was assessed. Overall, mirdametinib was well tolerated; no participants discontinued treatment because of a dose-limiting toxicity (DLT). One participant developed two treatment-related Grade 3 adverse events (AEs) (back and abdominal pain) simultaneously during Cycle 1; the pain resolved upon holding the drug and did not recur at the protocol-mandated reduced dose. There were no Grade 4 or 5 AEs. Five participants (26.3%) required dose reductions while on study: for Grade 3 abdominal and/or back pain (as described above), Grade 1 rash (n = 2), Grade 2 nausea (n = 1), and Grade 2 fatigue (n = 1). This study demonstrated activity of mirdametinib in participants with a PN with eight participants (42.1%; 95% confidence interval [CI]: 20%, 67%) responding to mirdametinib as defined by a ≥ 20% reduction of the target PN after 1 year of therapy.

Analysis of pharmacokinetic (PK) and pharmacodynamic (PD) data from samples collected during Study MEK-NF-201 is described in a separate PK/PD Analysis Plan which documents the integrated PK/PD analyses for mirdametinib.

Study Overview

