6.12.1.1 Adverse Events

Only TEAEs will be presented in summary tables, as defined in Section 4.2.2.1. An overview of these TEAEs will be presented by age cohort summarizing the number and percentages of participants with TEAEs; SAEs; TEAEs of at least Grade 3 severity; study-drug related AEs; and AEs leading to dose modification, interruption, reduction, and discontinuation. The number and percentage of participants with a maximum recorded toxicity Grade 1-5 will also be presented.

Separate summaries by SOC and PT will be provided for the incidence of TEAEs (also for TEAEs by PT only), incidence of TEAEs by highest severity, incidence of SAEs, TEAEs of at least Grade 3 severity, study drug-related TEAEs, study drug related SAEs, study drug-related TEAEs of at least Grade 3 severity, study procedure related TEAEs, TEAEs leading to discontinuation, most common TEAEs related to study drug (occurring in ≥5% of overall cohort), TEAEs leading to dose reduction, TEAEs leading to dose interruption and AESIs – all as defined in Section 4.2.2.1. In addition, a summary of TEAEs by PT only will also be presented. All summaries will present absolute participant counts (n) and TEAE event counts. Percentages (%) will be calculated based on the number of participants at risk. Additionally, TEAEs will be summarized by cycle of first onset (After Cycle 6, cycles will be grouped either as Cycles 7-12, or Cycle 13 and later).

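### The rule for repeated adverse events can pair one episode's grade with another episode's causality, so the drug-related Grade 3 or higher table can count participants who had no such event

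*SAP*

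**What the plan says.** SAP 4.2.1.2 sets two bases for reporting: "AEs will be reported on a per-participant basis and per-event". On the per-participant basis, repeats are merged: "events mapped to the same PT) during the study period, the event will be counted only once". The merged event then takes its attributes as follows: "In the latter case, the event will be assigned the worst severity and the strongest relationship to the study treatment". The opening words of that sentence are loose and could grammatically point to the per-event basis, but only repeated episodes of one term give the sentence a meaning. The sentence after it takes the earliest start and the latest stop, so the merged record is a composite by design.

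SAP 6.12.1.1 lists the summaries by SOC and PT. Most use one attribute (any event, highest severity, any drug-related event). One crosses severity with causality: "study drug-related TEAEs of at least Grade 3 severity". All summaries are to show both participant counts and event counts.

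SAP 4.2.1.1 defines relatedness event by event: "An AE will be classified as a study treatment-related AE if it has an investigator determination of related to study treatment". Protocol 10.3.3 likewise asks the investigator for a causality assessment of every occurrence. SAP 4.2.1.1 also pools adverse events over the Treatment and Long-Term Follow-up Phases, so the merging runs over the whole time on study.

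**The concern.** Taking the highest grade and the strongest causality separately does no harm in a table that uses only one of them. In a table defined by both, the merged record can meet the definition although no single episode does.

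Safety and tolerability is the first-listed secondary objective. The study is single-arm and uncontrolled, so investigator attribution is the main way its adverse event tables separate drug effect from disease. A count of drug-related severe events should therefore rest on events that an investigator judged both severe and drug-related. Repeats of one term have 24 cycles plus an open-ended follow-up phase in which to accumulate, which gives discordant episodes room to arise.

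**Working it through.** The plan states no figure on this point, so there is none to reproduce. The check applies the rule as written and compares it with a count in which grade and causality come from the same episode.

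**Inputs**
- Merging rule: highest grade and strongest causality over all episodes of one PT in one participant (SAP 4.2.1.2).
- Table definition: related and Grade 3 or higher, with participants and events both shown (SAP 6.12.1.1).
- Causality recorded for each event (SAP 4.2.1.1; Protocol 10.3.3).
- Planned size: 100 participants, 50 per age cohort (SAP 2.3).

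**Step 1: one participant, one PT, two episodes**

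Episode A is Grade 3 and unrelated. Episode B is Grade 1 and related.

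| Method | Grade | Related | Counted as related Grade 3 or higher |
|---|---|---|---|
| Rule as written | max(3, 1) = 3 | max(no, yes) = yes | 1 participant |
| Related episodes first, then highest grade | 1 | yes | 0 participants |
| Event count | each episode keeps its own | each episode keeps its own | 0 events |

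Under the rule as written, the PT row shows n = 1 with 0 events.

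**Step 2: which combinations produce this**

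Take two episodes, each of Grade 1 to 4 and either related or unrelated. That gives 8 × 8 = 64 ordered pairs.
- Pairs that the merged record classes as related Grade 3 or higher need at least one Grade 3 or 4 episode (3/4 of pairs) and at least one related episode (3/4 of pairs): 64 × 3/4 × 3/4 = 36.
- Pairs with at least one episode that is truly both: 64 × (1 − (3/4)²) = 64 × 7/16 = 28.
- False cases: 36 − 28 = 8. Each joins an unrelated Grade 3 or 4 episode to a related Grade 1 or 2 episode (2 × 2 combinations, in 2 orders).

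The merged count never misses a true case; it only adds false ones. The enumeration shows the mechanism. It does not estimate how often such pairs occur.

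**Step 3: scale**

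Let d be the proportion of participants who have, for some PT, an unrelated episode of Grade 3 or higher and a related milder episode, but no episode that is both. The expected number of false participants is N × d. The documents give no value for d, so the values below are assumed.

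| d (assumed) | N = 100 | N = 50 (one cohort) |
|---|---|---|
| 1% | 1 | 0.5 |
| 2% | 2 | 1 |
| 5% | 5 | 2.5 |

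These numbers apply in full to the PT rows. An SOC row gains a participant only if that person has no genuine related Grade 3 or higher event elsewhere in the SOC.

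**Step 4: does any text set the order of operations?**

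No section says whether events are selected on both attributes before merging or after it. SAP 6.12.1.1 refers to Section 4.2.2.1 for its definitions, but that section is Hematology, so the reference does not settle it.

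**The case against.** The strongest reply is that the miscount depends on an order that the SAP never prescribes. SAP 4.2.1.2 is a section on coding and counting. SAP 6.12.1.1 names its tables by type of event, and SAP 4.2.1.1 grades and attributes each event. A programmer who reads these together may well select the events that are both related and Grade 3 or higher, and only then count each participant once. That gives no false case. It is a fair reading, and the tables may be built that way. But the only rule the SAP states for a repeated term is the merge, and it carries no exception for crossed tables. Two competent programmers could produce different participant counts from this text.

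Three further points against the concern stand in full. The event count in the same table keeps each episode's own grade and causality, so a row with more participants than events would expose the artefact. The bias runs against the drug and hides no toxicity. And the crossed table is one of many SOC and PT summaries: neither the safety list in Protocol 9.4.2 nor the overview table in SAP 6.12.1.1 crosses causality with grade, so the main safety summaries are not distorted.

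A reader might try to size the problem from the earlier Phase 2 study of 19 participants. Protocol 2.1 reports Grade 3 toxicity in five, "with four of those subjects (21%) reporting a Grade 3 toxicity of pain". SAP 1.1 says: "One participant developed two treatment-related Grade 3 adverse events (AEs) (back and abdominal pain) simultaneously during Cycle 1". Subtracting one from four to obtain participants with unrelated Grade 3 pain is not supported. The two texts cite different reports of that study (2017 and 2021), and the Protocol does not call any of that pain unrelated. Back and abdominal pain are named separately, so pain cannot be treated as one PT, and the rule acts only within a PT. No source gives the share of such participants who also had a milder related episode. Protocol 10.3.1 further narrows the scenario by excluding expected symptoms of the studied disease from adverse events unless they are more severe than expected.

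**Conclusion.** The rule is wrong as written for the table of drug-related events of Grade 3 or higher, and the point is minor. Applied literally, it counts participants for whom no investigator reported an event that was both related and Grade 3 or higher. It can only overstate, and only the participant count in that crossed table. Tables of highest severity or of any drug-related event, the overview table, all event counts and the objective response analysis are unaffected.

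The size cannot be derived from the documents. It is one extra participant for each 1% of 100 participants with a discordant pair, and none if the programming already selects on both attributes before counting.

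A reader might infer that the rule misassigns seriousness in the same way and so distorts the table of drug-related SAEs. The text does not say that. SAP 4.2.1.2 assigns severity, relationship and dates to the merged event and is silent on seriousness, while SAP 4.2.1.1 defines a serious adverse reaction as a single serious event with a possible causal link. An error there would need a further programming step that the SAP does not describe.

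**What to change.** Add to SAP 4.2.1.2 that the rule of taking the highest grade and the strongest causality applies only to summaries defined by one attribute. For any table defined by two or more event attributes, in particular drug-related and Grade 3 or higher, the individual events that meet all the conditions are selected first, and each participant is then counted once per PT and once per SOC. This general wording also covers the drug-related SAE table, without implying that the rule is wrong there.

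In the same edit, correct the reference in SAP 6.12.1.1 from Section 4.2.2.1 to 4.2.1.1, where the adverse event definitions stand.

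The cost is one added statement, one corrected reference and a filter applied before the count. No new data are needed, and no other table changes. A programmed check that no row shows more participants than events would confirm that the filter works.
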